8.0 Research Plan and Procedures

8.1 HYPOTHESIS: Describe the hypothesis or what the study hopes to prove:

Our Hypotheses are:

1. Targeted Intermittent Oral Naltrexone (ION) will significantly reduce meth use, as determined by the proportion of meth-positive urine tests, compared to placebo.
2. Targeted ION will significantly reduce meth-associated sexual risk behavior, as determined by the audio computer assisted self-interview (ACASI) data and sexual risk behavior data, compared to placebo.
3. Targeted ION will significantly increase PrEP adherence among HIV-negative participants and ART adherence among participants living with HIV, as determined by drug levels and viral load testing; and sexual risk behavior data accounting for PrEP use and viral suppression, compared to placebo.

8.2 AIMS: List the specific aims:

Our Aims are:

1. To determine the efficacy of ION vs. placebo in reducing meth use, as determined by the proportion of meth-positive urine tests
2. To determine the efficacy of ION vs. placebo in reducing meth-associated sexual risk behaviors
3. To determine the efficacy of ION vs. placebo in increasing PrEP adherence among HIV-negative participants and ART adherence among participants living with HIV

8.3 DESIGN: Briefly describe the study design (e.g., observational, interventional, randomized, placebo-controlled, blinded, cross-over, cross-sectional, longitudinal, pharmacokinetic, etc.):

Research Design: This is a double-blind, placebo-controlled phase 2b trial in which 60 MSM who use meth will be randomly assigned (2:1) to receive 12 weeks of as-needed intermittent oral naltrexone 50 mg enhanced with an EMA-informed EMI platform, or receive as-needed placebo with EMA-informed EMI. The 12-week treatment period is consistent with other pharmacotherapy

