Sweat Testing: We will utilize tamper evident sweat patches (PharmChem, Inc., Fort Worth, Texas) that absorb perspiration 24 hours a day, for up to 10 days of continuous wear.¹⁸⁷ These patches will be tested for the presence of meth and meth metabolites, using testing procedures approved by the FDA since 1995.¹⁸⁷ PharmChek patch enzyme immunoassays to detect meth in sweat have been found to have 85% sensitivity and a 93% specificity rates, compared to gas chromatography-mass spectrometry.¹⁸⁸ At screening visits, we will affix patches on all participants. These patches have a semi-permeable membrane to allow oxygen, carbon dioxide and water vapor to pass through the patch, keeping the skin underneath sterile and healthy. We will replace the used patch worn since the prior visit and send those used patches for meth testing to PharmChem's laboratories. These patches will retain meth and meth metabolites for any use during the period it was worn. Hence, we anticipate no gaps in the window of detection for meth use.

PrEP and ART adherence: Among HIV-negative participants on PrEP and HIV-positive participants on ART, we will collect 20 ml. urine samples and test drug levels using a Urine Tenofovir immunoassay and RNA viral load from blood samples collected at baseline and monthly follow-up visits. For PrEP, good adherence will be defined as having tenofovir-diphosphate (TFV-DP) concentration of 1500 ng/ml, which has been classified as evidence of consistent dosing.^{182,183 184} Good ART adherence among participants living with HIV will be defined as having undetectable HIV viral load below 50 copies/ml.

Study drug adherence: The study will collect self-reported adherence via weekly modified TLFB assessments, similar to prior targeted naltrexone studies^{106,209} and via EMA for all participants.¹⁰⁹ Pill counts at weekly visits will also assess adherence. **MEMS caps** will be used to track medication adherence daily for as-treated analyses; each cap opening is recorded as an event in real time. MEMS have been shown to be reliable for adherence monitoring and have been used in our studies.^{66,124 109}

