Specific Aim 2: *To determine the efficacy of ION vs. placebo in reducing meth-associated sexual risk behaviors.* We will use GEE Poisson models with robust standard errors to assess evidence that the intervention reduces HIV risk behaviors, including number of sex partners, number of sex partners with whom meth is used and episodes of condomless sex with serodiscordant partners. *MDEs:* Using data from our prior trial on baseline means, within-subject correlation, and over-dispersion, we estimate that the study sample of 60 participants will have 80% power to detect ~46% net reductions in the numbers of sexual partners, ~67% reductions in partners with whom meth is used, and ~52% reductions in episodes of condomless sex with serodiscordant partners at 12 weeks. In our Project iN study, we have observed statistically significant reductions on sexual risk outcomes ranging between 85%-89% among the treatment arm, compared to placebo.¹⁰⁹ Therefore, given the results from the prior trial, we believe that the reductions we are powered to detect in this aim are reasonable to anticipate. *In sensitivity analyses*, we will examine how PrEP use and viral suppression status of participants and their partners (partner data assessed via self-reported egocentric data collection from participants)²¹⁹ modify treatment effects on sexual risk behaviors. We will also examine whether there is evidence of effect modification depending on whether both the study participant and partner, the

participant only, the partner only, or neither the participant nor the partner used a biomedical HIV prevention tool (PrEP or ART).²¹⁹

Specific Aim 3: *To determine the efficacy of ION vs. placebo in increasing PrEP adherence among HIV-negative participants and ART adherence among participants living with HIV, as measured by serum drug-levels and viral suppression rates.* We will use GEE Poisson models with robust standard errors to assess evidence that the intervention increases PrEP and ART adherence. *MDEs:* Using the assumptions for loss to follow-up from Project iN for Aim 1, we estimate that the study sample of 60 participants will have 80% power to detect 10-19 percentage point increases in PrEP/ART adherence, depending on within-subject correlations and adherence levels in the reference group.^{126,220}

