number of sex partners with whom meth is used and episodes of condomless sex with serodiscordant partners. *MDEs:* Using data from our prior trial on baseline means, within-subject correlation, and over-dispersion, we estimate that the study sample of 60 participants will have 80% power to detect ~46% net reductions in the numbers of sexual partners. In our Project iN study, we have observed statistically significant reductions on sexual risk outcomes ranging between 85%-89% among the treatment arm, compared to placebo.¹⁰⁹ Therefore, given the results from the prior trial, we believe that the reductions we are powered to detect in this aim are reasonable to anticipate. *In sensitivity analyses*, we will examine how PrEP use and viral suppression status of participants and their partners (partner data assessed via self-reported egocentric data collection from participants)²¹² modify treatment effects on sexual risk behaviors. We will also examine whether there is evidence of effect modification depending on whether both the study participant and partner, the participant only, the partner only, or neither the participant nor the partner used a biomedical HIV prevention tool (PrEP or ART).²¹²

Specific Aim 3: To determine the efficacy of ION vs. placebo in increasing PrEP adherence among HIV-negative participants and ART adherence among participants living with HIV, as measured by serum drug-levels and viral suppression rates. We will use GEE Poisson models with robust standard errors to assess evidence that the intervention increases PrEP and ART adherence. *MDEs:* Using the assumptions for loss to follow-up from Project iN for Aim 1, we estimate that the study sample with 60 participants will have 80% power to detect 10-19 percentage point increases in PrEP/ART adherence, depending on within-subject correlations and adherence levels in the reference group.^{126,220}

The sample size of 60 participants is the minimum number required to have sufficient power to determine the MDEs of intermittent naltrexone in reducing meth use for the phase 2b study.

11.4 * PARTICIPANT AGE RANGE: Eligible age ranges: (REQUIRED)

- 0-6 years
- 7-12 years
- 13-17 years
- 18-64 years
- 65+

11.5 * STUDY POPULATIONS: Data will be collected from or about the following types of people (check all that apply): (REQUIRED)

- Inpatients
- Outpatients
- Family members or caregivers
- Providers
- People who have a condition but who are not being seen as patients
- Healthy volunteers

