**MDEs:** Using data from our prior trial on baseline means, within-subject correlation, and over-dispersion, we estimate that the study sample of 54 participants will have 80% power to detect ~46% net reductions in the numbers of sexual partners and ~67% reductions in partners with whom meth is used. In our Project iN study, we have observed statistically significant reductions on sexual risk outcomes ranging between 85%-89% among the treatment arm, compared to placebo. Therefore, given the results from the prior trial, we believe that the reductions we are powered to detect in this aim are reasonable to anticipate.

**Specific Aim 3:** *To determine the efficacy of ION vs. placebo in increasing PrEP adherence among HIV-negative participants and ART adherence among participants living with HIV, as measured by serum drug levels and viral suppression rates.* We will use GEE Poisson models with robust standard errors to assess evidence that the intervention increases PrEP and ART adherence.

**MDEs:** Using the assumptions for loss to follow-up from Project iN for Aim 1, and informed by the within subject correlations of a PrEP adherence measure in the EPIC study and of detectable viral loads among HIV+ participants in a Mirtazapine trial for MSM who use meth, we estimate that the study sample of 54 participants will have 80% power to detect 10-19 percentage point increases in PrEP/ART adherence, depending on within-subject correlations and adherence levels in the reference group.

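### Aim 3 power is stated for the whole sample, but PrEP and ART adherence are measured in separate HIV groups, so one of them has at most half that number

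*SAP*

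**What the plan says.** The SAP's Aim 3 paragraph states that "the study sample of 54 participants will have 80% power to detect 10-19 percentage point increases in PrEP/ART adherence". Protocol 8.13 says "the study sample of 60 participants will have 80% power to detect 10-19 percentage point increases in PrEP/ART adherence", and protocol 11.3 says "the study sample with 60 participants will have 80% power to detect 10-19 percentage point increases in PrEP/ART adherence". All three add that the range depends on within-subject correlations and on adherence in the reference group. None gives a value for either.

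The aim, in protocol 8.2, is "To determine the efficacy of ION vs. placebo in increasing PrEP adherence among HIV-negative participants and ART adherence among participants living with HIV". Protocol 8.9 specifies the measurement: "Among HIV-negative participants on PrEP and HIV-positive participants on ART, we will collect 20 ml. urine samples". Good PrEP adherence is a tenofovir threshold of 1500 ng/ml. For the other group, "Good ART adherence among participants living with HIV will be defined as having undetectable HIV viral load below 50 copies/ml". Samples are taken at baseline and at the monthly visits.

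Randomization is 2:1 and stratified by HIV serostatus (protocol 8.9). No expected HIV split and no expected PrEP or ART uptake is given. The third inclusion criterion (11.7) can be met through condomless anal sex while using meth, so being on PrEP or ART is not an entry condition.

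**The concern.** The two outcomes belong to groups that cannot overlap, and they use different tests and thresholds. The whole sample therefore cannot be the denominator of either, unless everyone enrolled has the same HIV status. Yet a single power statement covers both and carries the trial total.

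A reader could take 80% power at 10-19 points to apply to the PrEP comparison and to the ART comparison alike. If the smaller comparison then came out null, it would be read as evidence against an effect of that size, when the trial had a much lower chance of showing one.

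**Working it through.** **Inputs.** N = 54 (SAP) or 60 (protocol 8.13, 11.3); 2:1 allocation (8.9). Two-sided 5% and 80% power are stated for Aim 1 and assumed here for Aim 3. The HIV split, drug uptake, Aim 3 correlations and reference adherence are not given.

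**1. Reproducing the plan's own figures.** The 10-19 range cannot be reproduced, because its n per outcome, correlations and reference rates are missing. Aim 1 can be approximately reproduced, and there 54 does act as the whole sample. A 24-point difference at 32% relative implies a reference of 0.24/0.32 = 75%. Take a linear effect over 13 weekly tests (0 to 12 weeks) with correlation 0.45:

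- Variance factor = (1 − 0.45)/(182/144) = 0.435.
- SE = sqrt(0.435 × (0.75×0.25/18 + 0.51×0.49/36)) = 0.0869.
- Power = Φ(0.24/0.0869 − 1.96) = 79%, against the stated 80%.

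This does not settle which n lies behind Aim 3.

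**2. Bound on n.** The groups are disjoint, so n(PrEP) + n(ART) ≤ N and the smaller is ≤ N/2. That is 27 of 54, about 18/9 by arm, or 30 of 60, about 20/10. It is lower if some participants take neither drug. No assumption about the HIV split is needed.

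**3. If 10-19 is a full-sample figure.** At 80% power the effect is 1.96 + 0.84 = 2.80 standard errors. Halving n multiplies the standard error by √2:

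- Power = Φ(2.80/√2 − 1.96) = Φ(0.02) = 51%.

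This does not depend on the correlation or the reference rate.

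**4. If 10-19 is a subgroup figure.** Consider the change from baseline to one follow-up visit, compared between arms. Each participant's change is −1, 0 or +1. For a mean gain d in the ION arm, Var = P(gain) + P(loss) − d². This is smallest when nobody loses adherence: d − d² = d(1 − d). Assume also that nobody changes on placebo, so that arm adds no variance. Then SE = sqrt(d(1 − d)/n), with n the number on ION.

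| n on ION | d | SE | Power = Φ(d/SE − 1.96) |
|---|---|---|---|
| 18 | 0.19 | 0.0925 | Φ(0.09) = 54% |
| 18 | 0.10 | 0.0707 | Φ(−0.55) = 29% |
| 20 | 0.19 | 0.0877 | Φ(0.21) = 58% |
| 20 | 0.10 | 0.0671 | Φ(−0.47) = 32% |
| 36 (whole sample of 54) | 0.19 | 0.0654 | Φ(0.95) = 83% |
| 36 (whole sample of 54) | 0.10 | 0.0500 | Φ(0.04) = 52% |

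At 19 points the smaller n alone takes the best case from above 80% to 54%. At 10 points a single-visit comparison falls short even with the whole sample, so that end would have to rest on some other form of analysis. These are normal approximations to an idealised case, and losses on ION or changes on placebo lower the power.

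**5. If the outcome is pooled.** For an indicator of adherence to one's own regimen, n is the number on either drug: at most 54 or 60, and fewer if some take neither.

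**The case against.** The strongest reply is that the range is a set of scenarios, not a single calculation. The statements make it conditional on correlation and reference adherence. The SAP also says that it was "informed by the within subject correlations of a PrEP adherence measure in the EPIC study" and "of detectable viral loads among HIV+ participants in a Mirtazapine trial for MSM who use meth". Separate sources suggest separate PrEP and ART calculations, possibly at subgroup sizes. That stands as a plausible account of where the range came from. It does not rescue the statement: the conditions named are correlation and reference rate, not sample size, and on this account the quoted 54 or 60 is not the n used.

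A second reply is that the outcomes may be pooled. The combined wording PrEP/ART and the single adherence rows in Tables 3 and 4 are compatible with that, and a near-full-sample n would then be legitimate. But no pooled outcome or model is defined, and the aim names two outcomes in two populations.

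A reader might infer that 10-19 points has been shown to be wrong. The documents do not support that. The inputs are missing, the pooled reading is open, and the bound in step 4 covers one follow-up visit, not an average over the three monthly visits. Nor do the documents support the inference that both outcomes are short of power, since the larger group may hold well over half the sample.

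**Conclusion.** The concern holds as a mismatch between the power statement and the outcomes it covers. It is certain that, analysed separately, one outcome has at most 27 of 54 (30 of 60), and that no n per outcome is stated.

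The loss of power is conditional. It is about 51% at the stated effect if the range is a full-sample figure. If the range is a subgroup figure, best-case power at 18/9 is about 54% at 19 points and 29% at 10, for a single-visit change with no change on placebo. Under pooling there may be little loss, but the outcome still has to be defined. This limits what Aim 3 can claim; the total of 60 is justified on meth use and does not depend on it.

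**What to change.** In SAP Aim 3 and protocol 8.13 and 11.3, replace the single claim with two minimum detectable effects, one for PrEP adherence and one for ART adherence. Give each at its own expected n per arm, with the retention, within-subject correlation and reference adherence used. Alternatively, if a pooled outcome was intended, define it, name its model, and give its detectable effect at the expected number on either drug.

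Two separate effects cost a rerun of the calculation and some wording, with no extra participants or tests. The downside is that the stated detectable effect becomes less favourable for the smaller group. Defining a pooled outcome is more than wording, because it fixes what Aim 3 estimates.
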